# 8.5.3.3 Management of results

Results from genetic testing will be obtained in a non-CLIA laboratory; therefore, results will not be provided back to the participant or health care provider for purposes of providing clinical diagnostic information.

## 8.5.3.4 Genetic counseling

Genetic counseling will not be provided under this protocol.

#### 8.6 SAFETY AND OTHER ASSESSMENTS

#### 8.6.1 Blood draw and laboratory screen

A blood draw and laboratory screen (e.g. Acute Care Panel, CBC+Diff, Hepatic Panel, LFT, TFT, HIV) will be conducted to screen for any medical condition that would increase risk for adverse events. Blood draw and laboratory screens will be conducted for screening and evaluation purposes.

## 8.6.2 Blood pressure

An assessment of blood pressure will be conducted as cardiovascular illness is an exclusion criterion for this study. Blood pressure will be collected for screening and evaluation purposes.

#### 8.6.3 Structural neuroimaging studies

Structural neuroimaging studies will be conducted within one year prior to study participation. In rare cases when an abnormality is discovered, participants are offered further assessment at the NIH via a neurology consult. Minor abnormalities with no clinical significance to participants may not be shared. Structural neuroimaging studies will be conducted for screening purposes.

#### 8.6.4 Electrocardiogram

The assessment of cardiovascular function via electrocardiogram (ECG) will be conducted as cardiovascular illness is an exclusion criterion for this study. ECG will be collected for screening purposes.

## 8.6.5 Heart rate

The assessment of heart rate will be conducted as cardiovascular illness is an exclusion criterion for this study. Heart rate will be collected for screening and evaluation purposes.

Additionally, heart rate will be collected during the study visit to monitor for potential adverse events.

## **8.6.6** Height

The assessment of height will be conducted for screening and evaluation purposes.

# 8.6.7 Medical history

A review of the participants medical history will be conducted. The review will involve the assessment of current medications as the use of psychoactive medications is exclusion criteria for this study. The review of medical history will also involve screening for medical conditions that would increase risk for MRI or any component of study participation. A review of medical history will be conducted for screening purposes.

# 8.6.8 Monitoring of clinical symptoms

Clinical Rating Scales will be used to monitor mood and anxiety symptoms. Additionally, clinical personnel with monitor participants for adverse events and other clinical symptoms (e.g. headache, nausea, vomiting, abdominal pain, chest pain, light-headedness, dizziness, and blurry vision).

# 8.6.9 Physical exam

Participants will undergo a physical exam to screen for medical conditions that would increase risk for MRI, TS-161, or any component of study participation. Physical exams will be conducted for screening purposes and safety assessment at the end of study participation.

## 8.6.10 Respiration

The assessment of respiration rate will be conducted to monitor responses to the administration of the study intervention.

# 8.6.11 Review of changes to Medical Report Form and Medication Review

Changes to participant's medical report forms and medication histories will be conducted to screen for medical conditions that would increase risk for the study intervention or other components of study participation. Review of changes to their medical report form and medication history will be performed in the 24 hours prior to administration of the study intervention.

#### **8.6.12** Temperature

The assessment of body temperature will be conducted to monitor responses to the administration of the study intervention.

#### 8.6.13 Urine pregnancy test

Women of child-bearing potential will undergo urine pregnancy testing to rule out pregnancy. Urine pregnancy tests will be completed at the time of screening and no more than 24 hours prior to start of each research condition and imaging procedure.

## **8.6.14** Urine toxicology

Participants will undergo a urine toxicology screen as drugs that act on the central nervous system is exclusion criteria for this study. Urine toxicology will be conducted for screening purposes.

## 8.6.15 Weight

Participants will undergo the measurement of their weight for screening purposes and at time points indicated in the Schedule of Events.

#### 8.7 ADVERSE EVENTS AND SERIOUS ADVERSE EVENTS

#### **8.7.1** Definition of Adverse Event

Adverse event means any untoward medical occurrence associated with the use of an intervention in humans, whether or not considered intervention-related (21 CFR 312.32 (a)).

## 8.7.2 Definition of Serious Adverse Events (SAE)

An AE or suspected AE is considered "serious" if, in the view of either the investigator or sponsor, it results in any of the following outcomes: death, a life-threatening adverse event, inpatient hospitalization or prolongation of existing hospitalization, a persistent or significant incapacity or substantial disruption of the ability to conduct normal life functions, or a congenital anomaly/birth defect. Important medical events that may not result in death, be life-threatening, or require hospitalization may be considered serious when, based upon appropriate medical judgment, they may jeopardize the participant and may require medical or surgical intervention to prevent one of the outcomes listed in this definition. Examples of such medical events include allergic bronchospasm requiring intensive treatment in an emergency room or at home, blood dyscrasias or convulsions that do not result in inpatient hospitalization, or the development of drug dependency or drug abuse.

#### 8.7.3 Classification of an Adverse Event.

#### 8.7.3.1 Severity of Event

For AEs not included in the protocol defined grading system, the following guidelines will be used to describe severity.

#### Mild

Events require minimal or no treatment and do not interfere with the participant's daily activities.

#### Moderate

Events result in a low level of inconvenience or concern with the therapeutic measures. Moderate events may cause some interference with functioning.

#### Severe

Events interrupt a participant's usual daily activity and may require systemic drug therapy or other treatment. Severe events are usually potentially life-threatening or incapacitating. Of note, the term "severe" does not necessarily equate to "serious".]

# 8.7.3.2 Relationship to Study Intervention

All AEs must have their relationship to study intervention assessed by the investigator who examines and evaluates the participant based on temporal relationship and their clinical judgment. The degree of certainty about causality will be graded using the categories below. In a clinical trial, the study product must always be suspect.

# **Definitely Related**

There is clear evidence to suggest a causal relationship, and other possible contributing factors can be ruled out. The clinical event, including an abnormal laboratory test result, occurs in a plausible time relationship to study intervention administration and cannot be explained by concurrent disease or other drugs or chemicals. The response to withdrawal of the study intervention (dechallenge) should be clinically plausible. The event must be pharmacologically or phenomenologically definitive, with use of a satisfactory rechallenge procedure if necessary.

## Probably Related

There is evidence to suggest a causal relationship, and the influence of other factors is unlikely. The clinical event, including an abnormal laboratory test result, occurs within a reasonable time after administration of the study intervention, is unlikely to be attributed to concurrent disease or other drugs or chemicals, and follows a clinically reasonable response on withdrawal (dechallenge). Rechallenge information is not required to fulfill this definition.

#### Potentially Related

There is some evidence to suggest a causal relationship (e.g., the event occurred within a reasonable time after administration of the trial medication). However, other factors may have contributed to the event (e.g., the participant's clinical condition, other concomitant events). Although an AE may rate only as "possibly related" soon after discovery, it can be flagged as requiring more information and later be upgraded to "probably related" or "definitely related", as appropriate.

#### Unlikely to be related

A clinical event, including an abnormal laboratory test result, whose temporal relationship to study intervention administration makes a causal relationship improbable (e.g., the event did not occur within a reasonable time after administration of the study intervention) and in which other drugs or chemicals or underlying disease provides plausible explanations (e.g., the participant's clinical condition, other concomitant treatments).

#### Not Related

The AE is completely independent of study intervention administration, and/or evidence exists that the event is definitely related to another etiology. There must be an alternative, definitive etiology documented by the clinician.

## 8.7.3.3 Expectedness

The PI and LIPs on the study will be responsible for determining whether an AE is expected or unexpected. An AE will be considered unexpected if the nature, severity, or frequency of the event is not consistent with the risk information previously described for the study intervention.

# 8.7.4 Time Period and Frequency for Event Assessment and Follow-Up

The occurrence of an AE or SAE may come to the attention of study personnel during study visits and interviews of a study participant presenting for medical care, or upon review by a study monitor.

All AEs including local and systemic reactions not meeting the criteria for SAEs will be captured on the appropriate CRF. Information to be collected includes event description, time of onset, clinician's assessment of severity, relationship to study product (assessed only by those with the training and authority to make a diagnosis), and time of resolution/stabilization of the event. All AEs occurring while on study must be documented appropriately regardless of relationship. All AEs will be followed to adequate resolution.

Any medical condition that is present at the time that the participant is screened will be considered as baseline and not reported as an AE. However, if the study participant's condition deteriorates at any time during the study, it will be recorded as an AE.

Changes in the severity of an AE will be documented to allow an assessment of the duration of the event at each level of severity to be performed. AEs characterized as intermittent require documentation of onset and duration of each episode.

LIPs on the study will record all reportable events with start dates occurring any time after informed consent is obtained until 7 (for non-serious AEs) or 30 days (for SAEs) after the last day of study participation. At each study visit, the investigator will inquire about the occurrence of AE/SAEs since the last visit. Events will be followed for outcome information until resolution or stabilization.

#### 8.7.5 Adverse Event Reporting

Reportable events for this protocol will be tracked and reported in compliance with Policy 801.

## 8.7.6 Serious Adverse Event Reporting

All serious adverse event (SAE) reporting will adhere to the U.S. Code of Federal Regulations (21 CFR Part 312.32) for IND drugs. The PI will immediately report any SAEs to the sponsor, whether or not these are considered study intervention-related, including those listed in the protocol or investigator brochure; any such report must include an assessment of whether there is a reasonable possibility that the study intervention caused the event. The PI or designee must send all SAEs on a MedWatch form to the Sponsor, copying the [contact] inbox at the time of awareness (within 24 hours for deaths, within 48 hours for all other SAEs). Additional information to include in the MedWatch Form 3500A is as follows:

- IND Number
- Protocol Number
- Principal Investigator's Name

#### • Event Attribution

The sponsor or designee will be responsible for determining if an SAE is reportable to the FDA as an IND Safety Report, i.e. the event is considered a serious unexpected suspected adverse reaction (SUSAR). The study sponsor will be responsible for notifying the Food and Drug Administration (FDA) or other applicable regulatory agency, of any unexpected fatal or life-threatening suspected AE as soon as possible, but in no case later than seven calendar days after the sponsor's initial receipt of the information. In addition, the sponsor must notify the FDA and all participating investigators of an Investigational New Drug (IND) safety report of potential serious risks, from clinical trials or any other source, as soon as possible, but in no case later than 15 calendar days after the sponsor determines that the information qualifies for reporting.

All SAEs will be followed until satisfactory resolution. All AEs will be documented on appropriate study records, including case report forms and AE tracking logs. All AEs will be provided in aggregate to the sponsor upon request and no less than once a year.

## 8.7.7 Events of Special Interest

Events of Special Interest are not applicable to this study.

# 8.7.8 Reporting of Pregnancy

Pregnant or nursing women or women who plan to become pregnant are excluded from this study. Participants who tested positive for pregnancy or become pregnant while enrolled in the study will be discontinued from the protocol and followed through pregnancy outcome.

#### 8.8 UNANTICIPATED PROBLEMS

## 8.8.1 Definition of Unanticipated Problems (UP)

Any incident, experience, or outcome that meets **all** of the following criteria:

- Unexpected in terms of nature, severity, or frequency given (a) the research procedures that are described in the protocol-related documents, such as the Institutional Review Board (IRB)-approved research protocol and informed consent document; and (b) the characteristics of the participant population being studied; and
- Related or possibly related to participation in the research ("possibly related" means there is a reasonable possibility that the incident, experience, or outcome may have been caused by the procedures involved in the research); and
- Suggests that the research places participants or others (which many include research staff, family members or other individuals not directly participating in the research) at a greater risk of harm (including physical, psychological, economic, or social harm) than was previously known or expected.

#### 8.8.2 Unanticipated Problem Reporting

The investigator will report unanticipated problems (UPs) to the NIH Institutional Review Board (IRB) as per Policy 801.

# 8.8.3 NIH Intramural IRB Reporting of IND Safety Reports

Only IND Safety Reports that meet the definition of an unanticipated problem will need to be reported to the NIH Intramural IRB.

#### 9 STATISTICAL CONSIDERATIONS

## 9.1 STATISTICAL HYPOTHESIS

## 9.1.1 Primary Endpoint

- Change from baseline in the MADRS total score
  - H0: The 95% confidence interval for the effect of drug (TS-161 minus placebo) on MADRS total at 3 weeks, after controlling for baseline scores, will include zero.
  - HA: The 95% confidence interval for the effect of drug (TS-161 minus placebo) on MADRS total at 3 weeks, after controlling for baseline scores, will be less than and exclude zero.

## 9.1.2 Secondary Endpoints

- Proportion of subjects in remission (defined as MADRS total score  $\leq 10$ ).
  - H0: The 95% confidence interval for the odds ratio (TS-161 versus placebo) predicting MADRS total score ≤10 at 3 weeks will include one.
  - HA: The 95% confidence interval for the odds ratio (TS-161 versus placebo) predicting MADRS total score ≤10 at 3 weeks will be greater than and exclude one.
- Proportion of subjects with response (defined as ≥50% reduction from baseline in MADRS total score).
  - H0: The 95% confidence interval for the odds ratio (TS-161 versus placebo) predicting 50% change from baseline in MADRS total score at 3 weeks will include one.
  - HA: The 95% confidence interval for the odds ratio (TS-161 versus placebo) predicting 50% change from baseline in MADRS total score at 3 weeks will be greater than and exclude one.
- Change from baseline in HDRS, BPRS, CADSS, C-SSRS, HAM-A, MADRS, PANAS, SHAPS, SSI, TEPS, YMRS total scores.
  - H0: The 95% confidence interval for the effect of drug (TS-161 minus placebo) on [all listed outcomes] at the timepoints listed in the Schedule of Events after controlling for baseline scores, will include zero.
  - HA: The 95% confidence interval for the effect of drug (TS-161 minus placebo) on [all listed outcomes] at the timepoints listed in the Schedule of Events after controlling for baseline scores, will be less than and exclude zero.

# 9.1.3 Surrogate Markers of Drug Effect, Target Engagement, and Antidepressant Response

- Change in MEG spectral power (gamma power).
  - H0: Among TRD-MDD subjects, pre-treatment gamma power levels will predict the magnitude of clinical improvement to TS-161, but not to placebo.
- Change in resting and task based functional connectivity in fMRI.
  - H0: Among TRD-MDD subjects, TS-161 administration will increase pgACC activity and decrease amygdala activity to emotional faces more than placebo. Similar effects will be observed in activity associated with the resting-state networks. TS-161 will also decrease pgACC activity during the tasks more than placebo.
- Change in glutamate levels in MRS.
  - H0: Among TRD-MDD subjects, pre-treatment mPFC glutamate levels will predict the magnitude of clinical improvement to TS-161 in subjects with MDD, but not to placebo.
  - HA: Among TRD-MDD subjects, post-treatment increases in glutamate levels will predict the magnitude of clinical improvement to TS-161 (but not placebo).
- Change in peripheral biomarkers (exploratory).

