# 2.2.3 Surrogate Neurobiological Markers of mGlu2/3 receptor antagonist TS-161's Mechanism of Action and/or Antidepressant Therapeutic Response

An impediment to progress in the discovery and testing of novel medications for serious psychiatric disorders is the lack of established surrogate neurobiological markers capable of predicting therapeutic response or identifying mechanisms of action. Identifying such markers may greatly facilitate drug discovery. The proposed project examines the utility of several potential neurobiological surrogate markers. A surrogate biomarker is most useful in that the number of subjects required to demonstrate an effect is less than that needed to prove clinical efficacy. Therefore, by assessing the same number of subjects with the neurobiological markers as those being evaluated for clinical efficacy, the proposed study should have sufficient power to identify surrogate neurobiological markers of practical significance. For example, previous studies from our laboratory found that gamma power changes, as determined by MEG, may be a putative biomarker to identify a subgroup of subjects with TRD who will respond favorably to ketamine's antidepressant effects (Cornwell, Salvadore et al. 2012, Nugent, Ballard et al. 2019).

In the proposed project, we will evaluate the following approaches as potential surrogate markers of drug effects and/or treatment response:

- 1. Gamma oscillatory power as well as other spectral analyses with MEG
- Resting and task based functional connectivity with fMRI. Resting and task based functional
- 3. Prefrontal glutamate levels (and other brain metabolites) measured with 7T 1H-MRS
- 4. Plasma/serum/Lymphocytes/mRNA for neurotrophic biomarkers

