## 9.4.7 Exploratory Analyses

We will conduct primary and secondary analyses as specified in Sections 9.4.2 and 9.4.3. We will not conduct exploratory analysis for confirmatory proof for registration trials.

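### Section 9.1.3 labels the expected marker effects as null hypotheses, Section 9.4 has no model that tests drug-specific prediction by MEG and MRS markers, and the marker power claim in Section 2.2.3 is not supported at n = 20

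*Combined protocol and SAP*

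**What the plan says.** Section 9.1.3 sets out hypotheses for three imaging markers.

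- **MEG gamma power.** H0 is that "pre-treatment gamma power levels will predict the magnitude of clinical improvement to TS-161, but not to placebo". No alternative is given.
- **fMRI.** H0 is that "TS-161 administration will increase pgACC activity and decrease amygdala activity to emotional faces more than placebo", with similar effects in resting-state networks, and that "TS-161 will also decrease pgACC activity during the tasks more than placebo". No alternative is given.
- **MRS glutamate.** H0 is that "pre-treatment mPFC glutamate levels will predict the magnitude of clinical improvement to TS-161 in subjects with MDD, but not to placebo". The alternative is that "post-treatment increases in glutamate levels will predict the magnitude of clinical improvement to TS-161 (but not placebo".

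Section 3 lists the same statements as the hypotheses the study expects to confirm. The MRS H0 and HA of Section 9.1.3 are its Hypothesis 1 and Hypothesis 2. Sections 9.1.1 and 9.1.2, by contrast, write each H0 as no effect: the interval includes zero, or includes one for odds ratios.

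On analysis, Section 9.4.2 models MADRS with a drug-by-time interaction, and Section 9.4.3 covers remission, response and the rating scales. Section 9.4.7 says only "We will conduct primary and secondary analyses as specified in Sections 9.4.2 and 9.4.3".

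On power, Section 2.2.3 concludes that "the proposed study should have sufficient power to identify surrogate neurobiological markers of practical significance". Its reason is that the marker sample is as large as the efficacy sample. Section 9.2 powers only the paired MADRS difference. Sections 8.4.2 and 8.4.3 head MEG and MRI/MRS as optional, and Section 8.4.3 expects some scans to be missed.

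**The concern.** A null hypothesis is what the analysis keeps when the data are weak. If H0 is the hoped-for effect, a small and noisy study keeps it by default. With no alternative, or one that concerns a different predictor, no rejection region is defined.

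Prediction on TS-161 but not on placebo is a statement about the difference between two associations. It needs one test of that difference. Without a planned test, the natural fallback is two separate tests, and non-significance on placebo in about 20 patients says little about absence of association.

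The power sentence moves a sample size from one estimand to another. Section 9.2 concerns a within-patient mean difference, whereas the MEG and MRS hypotheses concern the association between a marker and improvement. At stake are the trial's marker claims, including null results that could be over-read. The MADRS comparison is not at stake.

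**Working it through.** **1. The plan's own figure.** Inputs from Section 9.2: difference 7.5, d = 0.70, two-sided 5%, paired means. A noncentral-t calculation gives 19 patients for 80% power (82.3%); 20 patients give 84.4%. With SD of the difference 7.5/0.70 = 10.71, differences of 9.6 and 3.76 need 12 and 66 patients, against the stated 13 and 67. The primary sample size therefore reproduces to within one patient, but it says nothing about a correlation.

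**2. The hypotheses side by side.**

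| Marker | H0 in 9.1.3 | HA in 9.1.3 | Status in Section 3 |
|---|---|---|---|
| MEG gamma | Baseline predicts on drug only | None | Expected (Hypothesis 1) |
| fMRI | Activity changes more on drug | None | Expected (Hypothesis 1) |
| MRS glutamate | Baseline predicts on drug only | Post-treatment rise predicts on drug only | Both expected (Hypotheses 1 and 2) |

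No H0 is a no-effect statement and no pair is complementary. The second MEG hypothesis of Section 3, on post-treatment gamma increases, does not appear in Section 9.1.3.

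**3. Power for one marker–improvement correlation.** Fisher z, two-sided 5%: smallest r with 80% power = tanh[(1.960 + 0.842)/√(n − 3)].

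- n = 20: tanh(2.802/4.123) = 0.59
- n = 15: tanh(2.802/3.464) = 0.67

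The documents give no correlation, so a range is assumed. At n = 20, power is 25% (r = 0.3), 42% (0.4), 62% (0.5) and 82% (0.6). The n for 80% power, [2.802/atanh(r)]² + 3, is 85, 47 and 30 at r = 0.3, 0.4 and 0.5.

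**4. Two separate tests against one direct test.** Simulation with n = 20, 40,000 replicates per setting, one baseline marker per patient, and improvement on TS-161 and placebo in the same patients. The assumed correlation of improvement between periods is 0.3 to 0.5. The marker predicts equally on both treatments, so a drug-specific finding is false.

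| True r, both treatments | Significant on drug, not on placebo | Direct marker-by-drug test |
|---|---|---|
| 0.3 | 14–16% | 5% |
| 0.5 | 17–21% | 5% |
| 0.6 | 11–13% | 5% |

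When the true placebo correlation is 0.3, the placebo test alone is non-significant about 75% of the time.

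**5. Power of the direct test in this crossover.** The test relates the marker to the within-patient difference in improvement. With placebo correlation 0 and between-period correlation c, the relevant correlation is r/√[2(1 − c)]. For r = 0.6 and c = 0.3 it is 0.6/1.183 = 0.507. Then atanh(0.507) × 4.123 = 2.304, and 2.304 − 1.960 = 0.344, giving 63% power. For c = 0.5 it is 0.6, giving 82%.

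| r on TS-161 (placebo 0) | Fisher z, c = 0.3 to 0.5 | Simulation, same range |
|---|---|---|
| 0.6 | 63–82% | 66–84% |
| 0.5 | 46–62% | 48–64% |
| 0.3 | 19–25% | 19–25% |

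If the placebo correlation is 0.25 rather than 0 and r = 0.5, simulated power falls to 14–19%. These figures fit the pre-treatment hypotheses. Post-treatment change is measured separately in each period and was not simulated.

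**The case against.** The best defence is that Section 3 makes the intended direction plain, so the H0 labels look like a transcription slip. That is probably right. It explains the fault but does not remove it, because Section 9.1 is where the tests are defined.

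A second defence is that Section 2.2.3 is background text and may refer to drug-induced marker change, which the synopsis lists as the endpoint and for which a similar sample may suffice. This stands in part. But the same section speaks of markers that predict response, its example is gamma power identifying ketamine responders, and the MEG and MRS hypotheses in Section 9.1.3 are predictive. Section 2.2.5 itself calls MEG gamma exploratory.

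Some stronger readings are tempting but not supported:

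- **The plan would count a non-significant result as support, or intends separate tests by treatment.** No sentence says either. The first follows only from a literal reading of H0, and the second is a risk left open by the missing model. Section 9.4.3 drops thresholds for secondary outcomes, although it does not name the markers.
- **The missing interaction also affects fMRI.** It does not. That item is already a direct comparison with placebo; only its H0 label is wrong.
- **Either direction of pgACC change would confirm the hypothesis.** The directions are given by condition: up for emotional faces, down during the tasks. What is unclear is whether the tasks include the emotional-faces task.
- **Power for the drug–placebo contrast should be computed as for two independent groups.** At n = 20 that gives about 52% (r = 0.6) and 36% (r = 0.5), which ignores the crossover and is too low for the between-period correlations assumed here.

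**Conclusion.** The concern holds in this form. Three H0 statements in Section 9.1.3 are expected effects, two have no alternative, and the third has an alternative that is not its complement. This conflicts with Section 3 and with Sections 9.1.1 and 9.1.2. For MEG and MRS, no analysis in Section 9.4 tests the drug-specific claim. The end of Section 9.4.1 is cut off in the text available, but the same sentence is complete in Section 9.4.3 and describes no marker model.

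The claim of sufficient power is not supported for prediction. Twenty scanned patients suffice for one correlation only at about 0.59 or more. The direct test approaches or exceeds 80% only at r of about 0.6 with a between-period correlation near 0.5. Optional scans make fewer than 20 likely. The correlations are assumptions shown as ranges; the detectable values of 0.59 and 0.67 depend only on n, the 5% level and 80% power. The defect should be corrected, but it does not touch the primary conclusion.

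**What to change.** 1. In Section 9.1.3, give each marker a no-effect H0 and its complementary HA. Treat pre-treatment level and post-treatment change as separate pairs, and include the second MEG hypothesis from Section 3 or drop it openly.
2. For MEG and MRS, add to Section 9.4 a model of week-3 MADRS change with marker, drug, marker-by-drug, period and a random subject effect. H0 is a zero interaction. State which baseline scan is used, since one precedes each treatment phase, and which post-dose scan defines the change. Report the interaction with its 95% CI.
3. For fMRI, set H0 as no TS-161 minus placebo difference in activity, and say whether the tasks with a predicted pgACC fall include the emotional-faces task.
4. In Section 2.2.3, replace the sufficient-power sentence with the detectable correlation (0.59 at 20 scanned patients, 0.67 at 15), and say that null marker results are inconclusive.

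The cost is protocol and SAP wording, one added model and a less favourable power statement. No new data are needed, and the primary analysis and sample size do not change.
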